3.6.3 Full Analysis Set

The Full Analysis Set (FAS) will consist of all subjects in the ES who received at least one dose of study medication in AS0009 and have a valid measurement for at least one efficacy variable at any scheduled visit (excluding SFU visits) after AS0009 EV where efficacy is planned to be collected. This will include any data collected at an unscheduled or ET visit, and which has been remapped to a scheduled visit where efficacy data are planned. The protocol definition suggested that a valid measurement for at least one efficacy variable at AS0009 EV was required, but in order to identify subjects who have had assessments during AS0009, the requirement has been changed to ‘after’. This has been further clarified to include scheduled visits in AS0009 (where efficacy data is planned), excluding SFU visits, in order to ensure that all subjects in the FAS have data available to contribute to any of the efficacy analyses.

Secondary and other efficacy variables will be summarized for the FAS. Immunological variables will also be summarized on the FAS where specified in [Section 9.2](#).

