8.2 Week 4 (Visit 2) and Week 8 (Visit 3)

All procedures or assessments will be performed prior to administration of IMP.

- Concomitant medications
- Record AEs
- eG-SSRS
- Measure vital signs (temperature, pulse, and BP) Contact the IXRS
- Administer bimekizumab (after all other visit assessments are completed)

8.3 Week 12 (Visit 4), Week 24 (Visit 5), Week 36 (Visit 6), Week 72 (Visit 9)

The following procedures or assessments will be performed prior to administration of IMP, unless otherwise noted:

- Concomitant medications
- Record AEs
- eC-SSRS
- HADS
- ASQoL
- BASDAI
- BASFI
- SF-36
- PGADA
- Total and nocturnal spinal pain
- TB questionnaire
- Measure vital signs (temperature, pulse, and BP)
- Body weight
- MASES
- Obtain blood samples for:
 - Standard safety laboratory tests (hematology and biochemistry)
 - CRP
 - Anti-bimekizumab antibodies and bimekizumab plasma concentrations
- Perform a urine pregnancy test if there has been a delay in menses
- Contact the IXRS
- Administer bimekizumab (after all other visit assessments are completed)

8.4 Week 16, Week 20, Week 28, Week 32, Week 40, Week 44, Week 52, Week 56, Week 64, Week 68, Week 76, Week 80, Week 88, Week 92, Week 100, and Week 104

- Subjects will be given the opportunity for self-administration of bimekizumab. Adverse events will be captured spontaneously if the subject decides to visit the site to receive the bimekizumab administration.

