8.13 Week 208 (Visit 21)/Early Termination Visit

The following procedures or assessments will be performed:

- Concomitant medications
- Record AEs
- eC-SSRS
- HADS
- ASQoL
- BASDAI
- BASFI
- SF-36
- PGADA
- Total and nocturnal spinal pain
- TB questionnaire
- Measure vital signs (temperature, pulse, and BP)
- Body weight
- Physical examination (includes evaluation of signs and symptoms of active TB and risk for exposure to TB)

This document can not be used to support any marketing authorization application and any extensions or variations thereof.
REDACTED COPY

- MASES
- ECG
- Obtain blood samples for:
 - Standard safety laboratory tests (hematology and biochemistry)
 - CRP
 - Anti-bimekizumab antibodies and bimekizumab plasma concentrations
- Perform a urine pregnancy test if there has been a delay in menses
- Contact the IXRS

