13.1 Definition of analysis sets

The Enrolled Set (ES) will consist of all subjects who have given informed consent for AS0009.

The Safety Set (SS) will consist of all subjects who receive at least 1 dose of the IMP in AS0009.

The Full Analysis Set (FAS) will consist of all enrolled subjects who receive at least 1 dose of the IMP and have a valid measurement for at least 1 efficacy variable at AS0009 study entry.

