13.8 Handling of dropouts or missing data

Missing binary efficacy variables will be imputed using nonresponder imputation (NRI). In NRI, each subject with missing data or who has prematurely finished the study will be counted as a nonresponder.

For missing continuous efficacy variables, a multiple imputation (MI) approach will be used. In MI, the missing value is replaced by a set of plausible values, where each value is a Bayesian draw from the conditional distribution of the missing data given the observed data.

Non-monotone missing data (ie, intermittent missing data) will be imputed several times with the Markov Chain Monte Carlo (MCMC) method and monotone missing data will be imputed using

a monotone regression model. Each set of imputed data will then be summarized and the summaries will be combined into a single inference (Carpenter and Kenward, 2013).

Safety data will not be imputed.

As a sensitivity analysis, all efficacy variables will be analyzed based on observed data. Subjects with missing data or who have prematurely finished the study will be treated as missing.

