3.5 Mapping of assessments

Study assessments at an Early Termination (ET) visit where the visit date is within the protocol-defined visit window of a scheduled site visit will be mapped to that scheduled site visit (this does not include home visits). Visit windows will be calculated relative to the date of first dose in AS0009 (planned at the AS0009 EV), but if the dose was missed at that visit, the date of the AS0009 EV will be used instead. The following rules will also be applied:

- If there is an existing scheduled site visit in the window, and the specific assessment was performed at that scheduled site visit, then the relevant assessments at the ET visit will be mapped to the next scheduled site visit (regardless of whether this is within the protocol-defined visit window for that site visit).
- Study assessments at an ET visit that does not fall into the protocol-defined visit window of a scheduled site visit will be assigned to the next scheduled site visit after the date of the ET visit (regardless of whether this is within the protocol-defined visit window for that site visit).
- Mapping of an assessment to a scheduled visit will occur regardless of whether the assessment was planned to be conducted at that visit (with the exception of ADAb). For ADAb however, data will only be mapped to scheduled site visits where ADAb levels are planned to be measured. Any PK samples taken at the same ET visit will be mapped to the same scheduled visit as the ADAb.

- Additional rules regarding visit mapping are provided in [Section 8.1.5](#) for BASMI and [Section 9.1](#) and [Section 9.2](#) for PK and ADA_b summaries respectively.

Unscheduled assessments where the visit date is within the protocol-defined visit window of a scheduled site visit will be mapped to that scheduled site visit (this does not include home visits). Visit windows will be calculated relative to the date of first dose in AS0009. But if the dose was missed at that visit, the date of the AS0009 EV will be used instead. The following rules will also be applied:

- If there is an existing assessment with a non-missing response (from a scheduled site visit or ET visit) in the window, the assessment will be left as unscheduled.
- Unscheduled assessments which do not fall within a protocol-defined visit window based on time since first dose (or date of AS0009 EV if the first dose was missed) will be left as unscheduled.

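### Dosed subjects who leave before Week 12 can fall outside the SAP's FAS, so the Week 48 ASAS40 and ASAS20 analyses do not count them as non-responders

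*SAP*

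**What the plan says.** Protocol 13.1 defines the FAS as enrolled subjects who are dosed and "have a valid measurement for at least 1 efficacy variable at AS0009 study entry". Protocol 13.8 then says that under NRI "each subject with missing data or who has prematurely finished the study will be counted as a nonresponder".

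SAP 3.6.3 moves the requirement to after entry: the value must be "at any scheduled visit (excluding SFU visits) after AS0009 EV where efficacy is planned to be collected". ET or unscheduled data count only if remapped to a visit where efficacy is planned. One stated reason is "in order to identify subjects who have had assessments during AS0009"; the other is that every FAS subject should have data to contribute to the efficacy analyses.

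SAP 3.5 maps an ET visit to the site visit whose window contains it. An ET visit outside every window "will be assigned to the next scheduled site visit after the date of the ET visit". This applies whether or not the assessment was planned at that visit, and data that land on a visit where they were not planned are only listed. Antibody data are handled differently: "For ADAb however, data will only be mapped to scheduled site visits where ADAb levels are planned to be measured".

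SAP 4.2.1 restricts NRI to the FAS, and SAP 3.1 takes the analysis set as the denominator for percentages.

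**The concern.** ASAS40 and ASAS20 at Week 48 are two of the three secondary efficacy variables, and NRI is their primary missing-data method. Its purpose is to charge dropout against the response rate. An FAS that requires a value at Week 12 or later removes the earliest dropouts before NRI can act on them.

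Neither stated reason requires this. A subject seen at an ET visit by day 63 has been assessed during AS0009 and is still excluded. NRI needs no post-entry value, and SAP 4.2.1 even counts subjects with a missing baseline as non-responders. At stake is a modest upward shift in two response rates that will be read as long-term efficacy results.

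**Working it through.** The plan states no figure for this effect, so there is none to reproduce. The check has two parts.

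**1. Who falls outside the FAS**

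Inputs:
- Visit windows are ±7 days relative to first dose (SAP Table 2–1, footnote a).
- Site visits fall at day 0 (entry), 28 (Week 4), 56 (Week 8) and 84 (Week 12).
- Efficacy is planned at entry and Week 12 but not at Week 4 or Week 8 (SAP 2.2.2.3; Protocol 8.2).
- The ET visit collects PGADA, spinal pain, BASFI and BASDAI (Protocol 8.13). These supply all four ASAS20/40 domains.

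Applying SAP 3.5 to ET efficacy data, with entry efficacy already done:

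| ET visit, days after first dose | Mapped to | Efficacy planned there? | Qualifies for FAS? |
|---|---|---|---|
| 1 to 35 | Week 4 | No | No |
| 36 to 63 | Week 8 | No | No |
| 64 to 83 | Week 12 | Yes | Yes |

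The last excluded day is 56 + 7 = 63 days after first dose, which is relative day 64 under SAP 3.2.1. Attending Week 8 does not push the ET data on to Week 12. That rule applies only if the same assessment was performed at the scheduled visit, and efficacy is not assessed at Week 8.

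A subject who leaves before Week 12 with no ET efficacy value has nothing that qualifies. An unscheduled efficacy value inside the Week 12 window (from day 77) could rescue such a subject, but Protocol 8.15 lists no efficacy assessment at unscheduled visits.

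**2. Effect on the rate**

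Let N be the number of dosed subjects (the SS), R the Week 48 responders, and k the number in the SS but not in the FAS. Anyone in that group of k has no value at any planned efficacy visit after entry. Week 48 is therefore missing, and NRI on all dosed subjects would make the subject a non-responder. So R is the same in both analyses:

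- All dosed: R/N
- SAP FAS: R/(N-k)
- Ratio: N/(N-k)
- Excess in percentage points, with p = R/N: 100 × p × k/(N-k)

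The documents give neither k nor p. Assume N=285 (the stated maximum enrollment) and p from 0.5 to 0.8:

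| k | Factor N/(N-k) | Excess at p=0.5 | Excess at p=0.8 |
|---|---|---|---|
| 0 | 1 | 0 | 0 |
| 1 | 285/284 = 1.0035 | 50×1/284 = 0.18 | 80×1/284 = 0.28 |
| 2 | 285/283 = 1.0071 | 50×2/283 = 0.35 | 80×2/283 = 0.57 |
| 4 | 285/281 = 1.0142 | 50×4/281 = 0.71 | 80×4/281 = 1.14 |

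**3. Wording within the SAP**

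Section 3.6.3 requires a visit where efficacy is planned. Section 3.10 asks only for a value at a scheduled visit after entry, excluding the SFU. The exclusion reason in section 5.1 refers only to a value after study entry. On either looser wording, an ET value mapped to Week 4 or Week 8 could qualify. Section 3.6.3 is the most specific text and is used above, but the three do not match.

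**The case against.** The change of FAS is disclosed and explained in SAP 3.6.3, 3.10 and the amendment sections. SAP 5.1 plans counts for each analysis set and a listing of every excluded subject with the reason, so a reader can find k and restore the denominator. The study is single-arm and descriptive, with no formal sample size. Entrants have completed AS0008 and are expected to benefit, so few may leave within nine weeks. All of this stands, and it limits the weight of the point. It does not justify the exclusion, and the SAP does not discuss the effect on NRI.

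A reader might infer three stronger things that the documents do not support:

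- **That the SAP rate can only equal or exceed the rate in the protocol's FAS.** The SAP dropped the entry-value requirement, so its FAS is not a subset of the protocol's. Suppose 285 are dosed, k=0, and one subject has no entry value but has later data and is a Week 48 non-responder. The SAP rate is R/285 and the protocol rate R/284, so the SAP rate is lower. The upward direction holds only against all dosed subjects.
- **That the protocol FAS should be restored as primary.** It would drop subjects with usable Week 48 data because an entry value is missing, although response is measured against AS0008 Baseline.
- **That the FAS was narrowed because of the interim results.** The post-entry requirement dates from SAP Amendment 1. The planned-efficacy-visit restriction came in Amendment 3, after the interim review that Amendment 2 mentions, but Amendment 3 gives its own reason. Sequence alone does not show motive.

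**Conclusion.** The point holds in this form. On the wording of SAP 3.6.3, read with 3.5 and 4.2.1, two kinds of dosed subject are left out of the Week 48 ASAS40 and ASAS20 denominators: those whose only post-entry efficacy data come from an ET visit by day 63, and those who leave before Week 12 with no ET efficacy value. Protocol 13.1 and 13.8 would count them as non-responders if they had a valid entry value.

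Against all dosed subjects the bias is upward or nil. It is about 0.2 to 1.1 points for k of 1 to 4, and rests on the assumed N, p and k. No direction is claimed against the protocol FAS or for BASDAI, which uses multiple imputation. No test result changes, and the safety analyses use the SS and are unaffected. The change is worth making because it is cheap and removes a bias that runs one way.

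**What to change.** - Run the Week 48 ASAS40 and ASAS20 NRI analysis on all dosed subjects (the SS), at least as a sensitivity analysis beside the SAP FAS. Keep the planned-treatment columns used for the FAS, so that only the denominator changes.
- In SAP 3.6.3, let a valid ET efficacy value mapped to Week 4 or Week 8 count for FAS membership. It need not be displayed as a Week 12 result.
- Use one FAS definition in SAP 3.6.3, 3.10 and the exclusion reason in 5.1.

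The cost is SAP wording and one extra set of tables on data already held. Relative to the planned FAS analysis, the all-dosed rates will stay the same or be slightly lower.

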3.7 Treatment assignment and treatment groups

This is an open label, single arm study.

Treatment group at the completion of AS0008 (presented as ‘BKZ 160mg’ or ‘BKZ 320mg’) and an overall ‘BKZ Total’ column will be used to summarize data in AS0009.

The endpoints assessing maintenance of ASAS response over time will be summarized by treatment sequence across AS0008 and AS0009, and overall. Treatment sequences take the form ‘A/ B/ C’, where A is the treatment in the first 12 weeks of AS0008, B is the treatment from Week 12 to Week 48 of AS0008, and C is the treatment in AS0009. The eight planned treatment sequences are as follows:

- Placebo/BKZ 160mg/BKZ 160mg.
- Placebo/BKZ 320mg/BKZ 160mg.
- BKZ 16mg/BKZ 160mg/BKZ 160mg.

- BKZ 16mg/BKZ 320mg/BKZ 160mg.
- BKZ 64mg/BKZ 160mg/BKZ 160mg.
- BKZ 64mg/BKZ 320mg/BKZ 160mg.
- BKZ 160mg/BKZ 160mg/BKZ 160mg.
- BKZ 320mg/BKZ 320mg/BKZ 160mg.

Safety summaries including AS0009 data only will be presented by treatment group at the completion of AS0008 and overall. Safety summaries including data from both AS0008 and AS0009 combined will be presented for 'BKZ 160mg', 'BKZ 320mg', and 'BKZ Total', based on the SS for AS0009. Subjects who took bimekizumab 320mg during AS0008 will contribute to all three columns. Subjects who did not take 320mg in AS0008 will contribute to the 'BKZ 160mg' and 'BKZ Total' columns. The combined summaries will present data from AS0008 and AS0009 for the subjects who were enrolled in AS0009. The AS0009 only summaries will include only data collected in AS0009 (unless otherwise stated).

Subjects will be summarized and listed based on the actual/received treatment or the planned treatment for different analysis sets as follows:

- ES: planned treatment.
- SS and Sub-populations: actual treatment.
- FAS: planned treatment.

For actual and planned treatments in AS0008, the data will be used directly from the AS0008 analysis database without any rederivation of treatment assignments in each period.

In AS0009 it will be assumed that all subjects received the correct treatment as the dose level of bimekizumab is the same for all subjects and throughout the study (160mg). If a subject missed a dose at AS0008 Week 48, they will also be considered to have received the planned treatment. Thus for all subjects in AS0009 the actual treatment will be the same as the planned treatment.

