6 SELECTION AND WITHDRAWAL OF SUBJECTS

6.1 Inclusion criteria

To be eligible to participate in this study, all of the following criteria must be met:

- 1a. An Institutional Review Board (IRB)/Independent Ethics Committee (IEC) approved written Informed Consent Form (ICF) is signed and dated by the subject.
- 2a. Subject is considered reliable and capable of adhering to the protocol (eg, able to understand and complete questionnaires), visit schedule, or medication intake according to the judgment of the Investigator.
3. In the opinion of the Investigator, the subject is expected to benefit from participation in an OLE study.
4. Subject completed AS0008 without meeting any withdrawal criteria.
5. **Female** subjects must be postmenopausal, permanently sterilized (eg, tubal occlusion, hysterectomy, bilateral salpingectomy) or, if of childbearing potential (and engaged in sexual activity that could result in procreation), must be willing to use a highly effective method of contraception until 20 weeks after last administration of IMP, and have a negative pregnancy test at the last visit of AS0008. The following methods are considered highly effective when used consistently and correctly:
 - combined (estrogen and progestogen) hormonal contraception associated with inhibition of ovulation (oral, intravaginal or transdermal)
 - progestogen-only hormonal contraception associated with inhibition of ovulation (oral, injectable, implantable)
 - intrauterine device (IUD)
 - intrauterine hormone-releasing system (IUS)
 - bilateral tubal occlusion
 - vasectomized partner
 - sexual abstinence if it is in accordance with a subject's preferred and common lifestyle. Subjects who use abstinence as a form of birth control must agree to abstain from heterosexual intercourse until 20 weeks after the last dose of IMP. Study personnel must confirm the continued use of abstinence is still in accordance with the subject's lifestyle at regular intervals during the study.

Male subjects with a partner of childbearing potential must be willing to use a condom when sexually active, up until 20 weeks after the last administration of IMP (anticipated 5 half-lives).

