6.2 Exclusion criteria

Subjects are not permitted to enroll in the study if any of the following criteria are met:

1. Female subjects who plan to become pregnant during the study or within 20 weeks following the last dose of IMP. Male subjects who are planning a partner pregnancy during the study or within 20 weeks following the last dose.
2. Subjects with any current sign or symptom that may indicate a medically significant active infection (except for the common cold) or has had an infection requiring systemic antibiotics within 2 weeks of study entry. The medical monitor must be consulted prior to subject's entry into AS0009 in such cases.
3. Subjects who meet any withdrawal criteria in AS0008. For any subject with an ongoing SAE, or a history of serious infections (including hospitalizations) in the lead-in study, the Medical Monitor must be consulted prior to the subject's entry into AS0009.

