3.6.2 Safety Set

The Safety Set (SS) will consist of all subjects in the ES who received at least one dose of study medication in AS0009.

All safety variables will be summarized for the SS. Pharmacokinetic and immunological variables will also be summarized on the SS.

Two sub-populations of the SS will be defined for this study: Sub-population 1 will consist of all subjects in the SS who took no concomitant rescue medication in AS0009, and Sub-population 2 will consist of all subjects in the SS who took concomitant rescue medication in AS0009, as outlined in [Section 6.5](#). Rescue medications will be identified in the study database using the flag collected in the electronic case report form (eCRF). Concomitant medications are defined in [Section 6.4](#).

Selected summaries of the primary and secondary safety variables will be repeated for both SS Sub-populations only in the event that the number of subjects receiving rescue medication is $\geq 10\%$ of the total number of subjects in the SS.

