Exposure Category	Start date	End date	Duration of Exposure
Total exposure to BKZ 160mg	First dose of BKZ 160mg in AS0008 or AS0009	Last dose of BKZ 160mg in AS0009	Minimum of [(End date – start date + 140 ^a) +1] and (Date of last clinical contact ^b – start date + 1)
Exposure to BKZ 320mg	First dose of BKZ 320mg in AS0008	First dose of BKZ 160mg in AS0009 for subjects who were dosed in AS0009 ^c . Last dose of BKZ 320mg in AS0008 for subjects who were not dosed in AS0009	(End date – start date + 1) for subjects who were dosed in AS0009. Minimum of [(End date – start date + 140 ^a) +1] and (Date of last clinical contact ^b – start date + 1) for subjects who were not dosed in AS0009
Exposure to BKZ 160mg in AS0009	First dose of BKZ 160mg in AS0009	Last dose of BKZ 160mg in AS0009	Minimum of [(End date – start date + 140 ^a) +1] and (Date of last clinical contact ^b – start date + 1)
Subjects who died ^d	Start date for each option as above	Date of death	End date – start date + 1

BKZ=bimekizumab.

^a 140 days refer to 5 half-lives of BKZ.^b Date of last clinical contact for each subject is defined as the maximum of [last visit date including SFU visit (including unscheduled SFU visits), last AE start date (including imputed AE start dates), date of study termination or completion, last date of study drug administration following rules for partial treatment end dates as per Section 4.2.4].^c In the event that the first dose in AS0009 was more than 140 days after the last dose in AS0008, the exposure time at risk for 320mg will be calculated using AS0008 end date – AS0008 start date + 140 days.^d For subjects who died, the date of death will be used to replace the end date in the calculation of exposure time at risk only if the subject died within the ‘at risk’ interval (i.e., within 140 days following the last dose [not applicable for duration on BKZ 320mg] or if the subject died before dosing in AS0009 (for time at risk on BKZ 320mg). If the subject died more than 140 days after the last dose of BKZ in AS0009 the exposure time at risk will be calculated using the ‘at risk’ interval of 140 days. Note that date of death should be equivalent to date of last clinical contact.

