- Action taken with IMP: dose not changed, dose reduced, dose increased, drug temporarily, interrupted, drug permanently withdrawn or not applicable
- Outcome: resolving, not resolved, resolved, resolved with sequelae, worsened, fatal or unknown

AEs (including SAEs) are characterized as either non-treatment-emergent or treatment emergent according to the following criteria:

- Non-treatment emergent AEs are those with onset date after a 140-day period after the end date of study medication.
 - Any AE occurring more than 140 days after the last administration of study medication in AS0008 and prior to the first administration of study medication in AS0009 will also be considered as non-treatment emergent, and will therefore be excluded from the summary tables. Such events will be included in the listings.
- TEAEs are those with onset date on or after the start date of study medication in AS0009.
- Events that were ongoing at the end of AS0008 will have their treatment-emergent status taken from the AS0008 database.

For all AEs the following variables will be calculated (see [Section 10.2.1](#)):

- Duration.
- Time since first bimekizumab dose.
- Time since last/latest bimekizumab dose.

AE summaries will, in general, include only events with onset on or after the start date of study treatment in AS0009. Certain displays will be repeated including all AEs in AS0008 (with the exception of those with onset during placebo treatment) and AS0009 as outlined below. These displays will include only subjects from AS0008 who were enrolled in AS0009.

In general, the attributes of these events (for AEs that started and were resolved in AS0008) will be taken from the AS0008 database. However, the identification of Safety Topics of Interest will be made across all events in AS0008 and AS0009 using the criteria defined in this SAP.

For events which were ongoing at the end of AS0008, the following rules will be implemented:

- Onset date (and derived variables) will be taken from the AS0008 database
- End date, outcome, actions taken and seriousness will be taken from the AS0009 database.
- In order to ensure that AEs are not duplicated in the outputs these will be merged across the studies by Subject ID, verbatim term (AETERM), dictionary-derived term (AEDECOD), start date (AESTDTC), relationship (AEREL) and severity (AESEV) to create one record for the specific event.

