Summaries of AEs in AS0008 and AS0009 will include AEs with onset on the first dose of bimekizumab in AS0008 up to 140 days after the last dose of bimekizumab in AS0009. AEs which occur on the day of a treatment switch will be considered to have begun on the previous treatment, with the exception of the following AEs which will be considered to have begun on the new treatment:

- Events that fulfill the anaphylaxis criteria for acute events (see [Section 10.2.3](#)).
- Events that fulfill the hypersensitivity reaction criteria for (see [Section 10.2.3](#)).
- Events with a HLT of “Administration site reactions NEC”.
- Events with an HLT of “Injection site reactions”.

AEs which occur on the first day of bimekizumab treatment in AS0008 following initial treatment with placebo will not be included in the summaries, unless they fulfill 1 of the 4 exception criteria above. AEs which occur after the last dose of bimekizumab in AS0009 and up to 140 days after the last dose of bimekizumab in AS0009 will be assigned to bimekizumab 160mg.

AEs will be presented as “number of subjects (percentage of subjects) [number of events]”. “[number of events]” will include all cases of an AE including repeat occurrences in individual subjects, while “number of subjects” will count each subject only once.

An overview of TEAE (number and percentage of subjects with any TEAE, serious TEAE, TEAE leading to study discontinuation, TEAE leading to permanent withdrawal of study medication, drug-related TEAE, severe TEAE, fatal AE [see note below], fatal TEAE and TEAE with missing seriousness) will be provided by treatment group at completion of AS0008 and overall. This summary will be repeated by SS Sub-population. It will also be repeated including all TEAEs in AS0008 and AS0009 reported for subjects in the AS0009 SS (with the exception of those with onset during placebo treatment) combined.

The category for fatal AEs will be based on all subjects enrolled in AS0009 in all the above summaries.

The following categories of TEAE will be summarized by MedDRA SOC, HLT and PT, including EAIR and EAER (calculated as described in [Section 10.2.2](#)), where all summaries refer to AEs reported in AS0009 only except where stated:

- All TEAEs by treatment group at completion of AS0008 and overall.
- All TEAEs by treatment group at completion of AS0008 and overall, by SS Sub-population.
- Serious TEAEs by treatment group at completion of AS0008 and overall.

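### The combined AS0008 and AS0009 safety tables admit only AS0008 completers, so their 320 mg entries for fatal events and discontinuations are near zero by construction and cannot be compared with 160 mg

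*SAP*

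**What the plan says.** SAP 3.7 plans safety summaries that pool AS0008 and AS0009 in three columns (160 mg, 320 mg, total), "based on the SS for AS0009". It adds: "The combined summaries will present data from AS0008 and AS0009 for the subjects who were enrolled in AS0009". SAP 10.2 repeats the limit for the adverse event displays: "These displays will include only subjects from AS0008 who were enrolled in AS0009". For the TEAE overview it says: "It will also be repeated including all TEAEs in AS0008 and AS0009 reported for subjects in the AS0009 SS". SAP 3.6.2 defines the set: "The Safety Set (SS) will consist of all subjects in the ES who received at least one dose of study medication in AS0009".

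Entry is conditional. Protocol 6.1, criterion 4, requires: "Subject completed AS0008 without meeting any withdrawal criteria". Protocol 6.2, criterion 3, excludes: "Subjects who meet any withdrawal criteria in AS0008".

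The combined displays are:
- an exposure table (SAP 10.1);
- the TEAE overview, which has rows for fatal events, TEAEs leading to study discontinuation and TEAEs leading to permanent drug withdrawal (SAP 10.2);
- all TEAEs and serious TEAEs by dose at onset, with EAIR and EAER (SAP 10.2).

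The SAP states the restriction openly. It attaches no caveat about selection and plans no combined table on everyone who took bimekizumab in AS0008.

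**The concern.** Pooling the lead-in with the extension is meant to show safety by dose from first exposure. Here a subject's AS0008 time counts only if that subject finished AS0008 and went on. Anyone who died in AS0008, or left it because of an adverse event, is absent from both numerator and denominator.

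The restriction bears unequally on the doses. AS0009 gives 160 mg to everyone, so 320 mg time can come only from AS0008. The rows that describe leaving the study then contrast a dose at which leaving has been conditioned away with a dose at which it is observed for up to four years. A reader comparing adjacent columns would not see this from the table.

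**Working it through.** The plan gives no rate, sample size or power for these tables, so there is no figure to reproduce. The check traces the rules and then does what arithmetic is possible.

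**1. Who is in.** A subject in the combined tables has received an AS0009 dose (SAP 3.6.2), and so had to complete AS0008 without meeting a withdrawal criterion (Protocol 6.1, 6.2).

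**2. What the 320 mg column holds.** SAP Tables 10-1 and 10-2 start 320 mg time at the first 320 mg dose in AS0008 and end it at the first 160 mg dose in AS0009. SAP 10.2 assigns events to treatment at onset, and events after the last AS0009 dose to 160 mg. Completer time is therefore 100% of 320 mg time at risk.

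**3. Share in the other columns.** For a subject who completes AS0009, time at risk in AS0009 is 204 + 20 = 224 weeks. Bimekizumab time before entry is 36 or 48 weeks (SAP 2.2.1.3). With share = w / (w + 224):
- w = 36: 36/260 = 13.8%
- w = 48: 48/272 = 17.6%

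This applies to the total column, and to the 160 mg column for subjects who never took 320 mg and had w weeks at 160 mg in AS0008.

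**4. What can still reach the 320 mg rows for death and discontinuation.**
- An event that starts on 320 mg, is ongoing at roll-over and later leads to death or withdrawal. Its outcome and action come from the AS0009 database.
- An event starting on the day of the switch, which goes to the previous treatment, with listed exceptions such as injection site reactions.
- A death after consent but before dosing, because the fatal AE row uses all enrolled subjects.

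SAP 10.2.1 also treats onset up to 140 days after the last dose of a treatment as during that treatment, for the time-since-first-dose variable. Used to assign columns, that would reach about 140 − 28 = 112 days into AS0009 and contradict the Table 10-2 end date. The two passages need reconciling.

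**5. Illustration in counts, because the overview prints counts and percentages.** The documents give neither the 320 mg group size nor an event rate. Assume N = 100 or 150 and a true rate r of death or adverse event withdrawal of 2 to 8 per 100 patient-years. Subjects lost = N × (1 − exp(−rT)), with T = 36 × 7/365.25 = 0.690 or 48 × 7/365.25 = 0.920 years:

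| N | r = 2 | r = 4 | r = 8 |
|---|---|---|---|
| 100 | 1.4 to 1.8 | 2.7 to 3.6 | 5.4 to 7.1 |
| 150 | 2.1 to 2.7 | 4.1 to 5.4 | 8.1 to 10.6 |

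The upper ends need everyone on 320 mg for 48 weeks. Only one of the four planned 320 mg sequences in SAP 3.7 gives that; the other three give 36. If events take 2 to 4 weeks from onset to outcome (assumed), the number carried over roll-over is (N − lost) × (1 − exp(−r × lag)), or 0.1 to 0.9 subjects across these settings. This shows the mechanism; it does not estimate the loss.

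**The case against.** **Scope.** The primary and secondary safety variables rest on AS0009-only tables. The protocol's safety section asks for no combined tables; SAP Amendment 1 added them and states their population. This stands. It limits the point but does not repair the by-dose cells.

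**Rates.** The overview gives numbers and percentages, and the separate tables of fatal TEAEs and of TEAEs leading to withdrawal are by treatment group at completion of AS0008, so they are AS0009 displays. A reader might infer that a withdrawal rate per 100 patient-years is biased in print. No combined table by dose reports one. EAIR and EAER appear only in the combined TEAE and serious TEAE tables.

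**Table 10-2.** The 320 mg rule has a branch, "Last dose of BKZ 320mg in AS0008 for subjects who were not dosed in AS0009", which might be read as the remains of a plan to include AS0008 dropouts. SAP 4.2.4 expressly foresees subjects who end AS0009 without a dose, and the branch fits them. It is not evidence of such a plan.

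**Numbers excluded.** Setting 303 AS0008 subjects (Protocol 2.1.1.1) against up to 285 in AS0009 (Protocol 13.10) suggests at least 18 excluded. But 285 is a planning ceiling and 303 an achieved number, so the difference is not a dropout count. Those who did not enter may have been on placebo, 16 mg or 64 mg, and no AS0008 death or adverse event withdrawal on 320 mg is documented.

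**Remedy.** An all-treated table puts people who never consented to AS0009 into an AS0009 report, and pooling may belong in a later integration. That is a fair argument about placement. It does not justify printing 320 mg cells that are almost empty by rule.

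**Conclusion.** The point holds for the combined tables. The 320 mg overview entries for fatal TEAEs and for TEAEs leading to study discontinuation or drug withdrawal are near zero by construction, though not exactly zero, and cannot be compared with 160 mg. This assumes that the AS0009 entry criteria were followed.

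For all TEAEs and serious TEAEs, the rule drops every bimekizumab event and all bimekizumab time of subjects who did not roll over. That lowers rates where such events led to exit. A reader might go on to infer that 320 mg will look safer than 160 mg overall. The documents do not support this. Completers' non-fatal events in AS0008 are kept, the 160 mg subjects passed the same completion filter, and 320 mg covers only the first 48 weeks. If events are commoner early in treatment, 320 mg could look worse, so the net direction is unknown.

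The size cannot be computed, because actual AS0009 enrolment, reasons for non-entry and the 320 mg group size are not given.

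**What to change.** In SAP 3.7, 10.1 and 10.2:

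1. Add a version of the combined exposure, overview, all-TEAE and serious TEAE tables on all AS0008 subjects with at least one bimekizumab dose. Table 10-2 already has a 320 mg rule for subjects not dosed in AS0009; add matching 160 mg and total rules, and corresponding duration rules in Table 10-1. State that a subject who took only 16 mg or 64 mg counts in the total column alone.
2. In the AS0009-enrollee version, omit the 320 mg cells for fatal events and discontinuations, and footnote that all AS0008 time is conditional on completing AS0008.
3. Reconcile the 140-day wording in SAP 10.2.1 with the Table 10-2 end date.

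The cost is SAP wording and extra programming; AS0008 is complete and its database already feeds these tables. The added tables will have an N larger than the AS0009 Safety Set and need a title that says so.
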